# **6.6.4** Dose Modification for Specific Adverse Events

## 6.6.4.1 Immune-related Adverse Events (irAEs) – For Part 1B Only

Guidance for BNT411 dose modification and management of irAEs is provided in the Table 6-1 below. For Grade 1 irAEs, trial treatment should be continued with close monitoring. Corticosteroids taper should be initiated over the course of at least 4 to 6 weeks when the irAE improves to Grade ≤1. Permanent discontinuation of trial treatment is recommended with Grade 4 toxicities with the exception of endocrinopathies that have been controlled by hormone replacement. Trial treatment should also be permanently discontinued for any Grade 3 irAE that recurs and for any life-threatening irAE. For additional guidance on the recommended management of irAEs, please refer to the *Management of Immune-Related Adverse Events in Patients Treated with Immune Checkpoint Inhibitor Therapy: American Society of Clinical Oncology Practice Guideline* (Brahmer et al, 2018). Furthermore, guidelines for the monitoring and management of potential cytokine release syndrome (CRS) can be found in Attachment 12.1.

BioNTech SE BNT411-01 Version 6.0

Table 6-1: BNT411 Dose Modification and Management of irAEs

Immune-related AEs	Toxicity Grade (CTCAE v5.0)	Dose Modification	Guidance for Management of irAEs
Pneumonitis	Grade 1-2 Grade 3 or 4	1st occurrence If there is radiographic evidence of pneumonitis progression, hold treatment until there is evidence of improvement/ resolution to Grade 1 or less¹  2nd occurrence: Permanently discontinue  Permanently discontinue	Monitor for signs and symptoms of pneumonitis  Evaluate for pneumonitis with radiographic imaging  For Grade ≥2:  Consider initiation of corticosteroid treatment (initial dose of 1-2 mg/kg prednisone or equivalent followed by taper).  Corticosteroid taper should be initiated when the irAE improves to Grade ≤1
Colitis	Grade 2	Hold treatment until resolved to baseline 	Monitor for signs and symptoms of colitis. Consider
Contis			gastroenterology consultation and confirm diagnosis of colitis
Grade 3 Grade 4		Refer to Sections 6.6.3.1 and 6.6.3.2  Permanently discontinue	Consider administration of corticosteroids (initial dose of 1-2 mg/kg prednisone or equivalent) followed by taper Corticosteroid taper should be initiated when the irAE
		improves to Grade ≤1	
T1DM or Hyperglycemia	Newly diagnosed T1DM or Grade 3-4 hyperglycemia	Refer to Sections 6.6.3.1 and 6.6.3.2	Monitor for hyperglycemia or other signs and symptoms of diabetes Consider endocrinology consultation Consider administration of insulin for type 1 diabetes Consider administration of anti-hyperglycemic medication in patients with hyperglycemia
Hypophysitis	Grade 2	Continue treatment at the discretion of the investigator	Monitor for signs and symptoms of hypophysitis. Consider endocrinology consultation Consider administration of corticosteroids and initiate hormonal replacements as clinically indicated. Corticosteroid taper should be initiated upon irAE improving to Grade ≤1
	Grade 3 or 4	Refer to Sections 6.6.3.1 and 6.6.3.2	
Hyperthyroidism	Grade 2	Continue treatment at the discretion of the investigator	Monitor for signs and symptoms of thyroid disorders Consider management with thionamides and beta-blockers as appropriate
	Grade 3-4	Refer to Sections 6.6.3.1 and 6.6.3.2	
	Grade 2	Continue treatment at the discretion of the investigator	Monitor for signs and symptoms of thyroid disorders. Consider endocrinology consultation
	Grade 3-4	Refer to Sections 6.6.3.1 and 6.6.3.2	Consider initiation of thyroid replacement hormones per standard of care

BioNTech SE BNT411-01 Version 6.0

Immune-related AEs	Toxicity Grade (CTCAE v5.0)	Dose Modification	Guidance for Management of irAEs	
Nephritis and Renal Dysfunction	Grade 1	Consider temporary hold pending consideration of baseline renal function and to confirm etiology 	Monitor for changes in creatinine levels  For Grade ≥2:  — If worsening or no improvement, consider	
	Grade 2	Hold treatment until resolved to baseline 	administration of corticosteroids (prednisone 1-2 mg/kg or equivalent) followed by taper  - Corticosteroid taper should be initiated upon irAE improving to Grade ≤1	
	Grade 3-4	Permanently discontinue		
Skin Adverse Reactions	Grade 1-2	Continue treatment at the discretion of the investigator	Based on the severity of the adverse reaction, consider administration of corticosteroids. Corticosteroid taper should be initiated upon irAE improving to Grade ≤1  For signs or symptoms of SJS or TEN, withhold and refer the patients for specialized care. If SJS or TEN is confirmed, permanently discontinue	
	Grade 3	Refer to Sections 6.6.3.1 and 6.6.3.2		
	Grade 4	Permanently discontinue		
All other immune-related AEs	Grade 2	Continue treatment at the discretion of the investigator	Based on type and severity of AE, consider administration of corticosteroids. Permanently discontinue for any Grade 3 irAE that recurs and for any life-threatening irAEs	
	Grade 3	Refer to Sections 6.6.3.1 and 6.6.3.2 and or discontinue based on the type of event.		
	Grade 4	Permanently discontinue		

<sup>1 The next dose of BNT411 can maximally be delayed for 21 days unless approved otherwise by the sponsor's medical monitor. If irAE resolves within 21 days to baseline, restart treatment at the same dose level after consultation with the sponsor's medical monitor.

AE, adverse event; irAEs, immune-related AEs; CTCAE, Common Terminology Criteria for Adverse Events; T1DM, type 1 diabetes mellitus; SJS, Steven Johnsons Syndrome; TEN, toxic epidermal necrolysis

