# Note: Grade 4 AEs fulfilling DLT criteria will always lead to BNT411 discontinuation.

# First occurrence of AE fulfilling DLT criteria Grade 3:

- As a first measure, administration of BNT411 needs to be withheld.
- Investigator must contact sponsor for thorough discussion in order to decide whether the patient should be withdrawn from BNT411 treatment or next dosing should be delayed.
- Administration of BNT411 can be delayed for up to 21 days (i.e. one cycle) unless otherwise approved by the sponsor's medical monitor. If the intensity resolves to Grade ≤1 or baseline within this period, re-treatment may be considered under the following circumstances:
  - Sponsor and investigator will discuss any safety concerns in order to decide whether the next dose of BNT411 should be administered at the same dose level or one dose level lower (DL-1). Intermediate dose levels defined in the protocol may also be considered. The sponsor may also consult the SRC.

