# Second occurrence of an identical AE Grade 3 after re-exposure to BNT411:

- As a first measure, administration of BNT411 needs to be withheld.
- If re-treatment leads to an identical AE with the same intensity, the next administration of BNT411 can be delayed for up to 21 days unless otherwise approved by the sponsor's medical monitor. If the intensity of the AE resolves to Grade ≤1 or baseline within this period, re-treatment may be considered under the following conditions:
  - The next dose of BNT411 should be administered at one dose level lower (DL-1 or DL-2) than the dose level causing the recurrence of the AE.
     Intermediate dose levels defined in the protocol may be considered.

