# Third occurrence of an identical AE Grade ≥2 after re-exposure to BNT411:

- As a first measure, administration of BNT411 needs to be withheld.
- If re-treatment at a lower dose leads to a third identical AE with intensity Grade ≥2, the patient must permanently discontinue trial drug. No dose delay is allowed. However, if the AE is Grade ≤1 or baseline, re-treatment may be considered under the following condition:
  - Next dose of BNT411 should be administered at the same reduced dose level (DL-1 or DL-2).

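### Part 1B: Protocol 6.6.4.1 stops treatment when a Grade 3 irAE recurs, but six Table 6-1 rows point to 6.6.3.2, which allows BNT411 re-treatment at a lower dose

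*Protocol*

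**What the plan says.** Protocol 6.6.4.1 applies to Part 1B only. Its opening text gives a general rule for recurrence: "Trial treatment should also be permanently discontinued for any Grade 3 irAE that recurs". The rule makes no exception by type of event and offers no lower dose. The last row of Table 6-1, for all other irAEs, repeats it: "Permanently discontinue for any Grade 3 irAE that recurs and for any life-threatening irAEs".

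Six other rows of Table 6-1 handle Grade 3 with a pointer only: "Refer to Sections 6.6.3.1 and 6.6.3.2". These are colitis, T1DM or hyperglycemia, hypophysitis, hyperthyroidism, the row managed with thyroid replacement hormone, and skin reactions. None of the six says what to do if a Grade 3 event comes back.

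Section 6.6.3.2 covers Part 1B events that meet DLT criteria after the DLT period. It has three steps.

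- First Grade 3 event: "As a first measure, administration of BNT411 needs to be withheld". The investigator must then discuss the case with the sponsor, and dosing may resume after recovery.
- Second identical Grade 3 event: BNT411 can be delayed for up to 21 days. If the event recovers to Grade 1 or baseline, "re-treatment may be considered under the following conditions", at a reduced dose level (DL-1 or DL-2).
- Third identical event of Grade 2 or higher: "the patient must permanently discontinue trial drug. No dose delay is allowed".

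**The concern.** Take a Part 1B patient with a Grade 3 irAE that meets DLT criteria after Cycle 1, recovers, and returns identically on re-exposure. The text of 6.6.4.1 says to stop. The table row in the same section sends the site to 6.6.3.2, whose second-occurrence step fits the case and allows BNT411 at a lower dose. On recurrence count alone, 6.6.3.2 requires a stop only at the third event.

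This is a first-in-human combination with atezolizumab, which the protocol names as a known source of irAEs (2.3.2). A patient whom one rule would stop could be dosed again under the other, and two sites could treat the same event differently.

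**Working it through.** There is no figure in the plan to reproduce. The check sets the rules side by side, counts table rows, and then asks which rows can really meet the conflict.

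**Same event, two routes (second identical Grade 3 irAE, Part 1B, after Cycle 1)**

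| Source | Action |
|---|---|
| 6.6.4.1 text | Stop trial treatment permanently |
| Table 6-1, six rows | Pointer to 6.6.3.1/6.6.3.2, silent on recurrence |
| 6.6.3.2, second occurrence | Delay, then lower-dose re-treatment may be considered |
| 6.6.3.2, third occurrence | Mandatory stop at Grade 2 or higher |

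The 6.6.4.1 rule speaks of trial treatment, which under 6.1 can include all four drugs. Section 6.6.3.2 governs BNT411, so the conflict is about BNT411.

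**Row count**

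- Rows in Table 6-1: pneumonitis, colitis, T1DM/hyperglycemia, hypophysitis, hyperthyroidism, thyroid replacement, nephritis, skin, all other = 9.
- Stopped at the first Grade 3 event: pneumonitis and nephritis = 2.
- Grade 3 pointer to 6.6.3.1/6.6.3.2: 9 − 2 = 7.
- Pointer rows that repeat the recurrence stop: all other = 1.
- Pointer rows without it: 7 − 1 = 6.

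**Do irAEs fall within 6.6.3.2?** Yes. The Part 1B DLT criteria in 6.6.2 include Grade 3 colitis, and other Grade 3 irAEs, that do not downgrade within the stated 3-day or 14-day limits.

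**Which of the six rows are exposed in practice?** Four are endocrine (T1DM/hyperglycemia, hypophysitis and two thyroid rows), which leaves 6 − 4 = 2, colitis and skin. In the endocrine rows, asymptomatic managed Grade 3 endocrinopathy is excluded from the DLT criteria by 6.6.2 and so lies outside 6.6.3.2. Newly diagnosed T1DM cannot recur. Symptomatic Grade 3 endocrine events and Grade 3 hyperglycemia remain, if they meet DLT criteria.

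**Do other sections settle it?** Section 7.1.2 on rechallenge sends re-treatment to 6.6.3.1 and 6.6.3.2 and does not mention 6.6.4.1. The individual stopping list in 6.6.5 names a second Grade 3 or higher infusion reaction but no recurrent Grade 3 irAE. Its first item covers any event fulfilling DLT criteria, but its second deals separately with events after the DLT period and stops those for failure to resolve, or for a long delay.

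**Effect on analysis.** Section 6.6.3.2 starts after the DLT period, so Cycle 1 DLT counts and the MTD rule are untouched. The first-event hold is a temporary withdrawal under Protocol 10.3.3, so the patient already counts in the combined dose-reduction and interruption category of SAP 8.5.2. The permanent-discontinuation count, and the separate dose-reduction count in SAP 8.5.1, can each move by at most that one patient. The discontinuation count does not move if the patient later stops at a third event.

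**The case against.** The strongest reply is that the texts can be read together. Section 6.6.4.1 is the specific rule, for irAEs in Part 1B, and says treatment should stop. Section 6.6.3.2 is general and only permits re-treatment. A specific stop limits a general permission, stopping satisfies both sections, and the stop sentence stands in the same section as the pointers. This reading is reasonable and probably intended. However, no text shown sets that precedence, and a site that starts from the table row or from 7.1.2 is led to the permissive step.

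The path is also narrow. The event must meet DLT criteria, recover, return at the same intensity and recover again. The sponsor is consulted at the first event, and 6.6.3.2 stops BNT411 when causality cannot be attributed among the four drugs. This narrows the path without closing it: an attributed irAE stays on it, and sponsor contact is not expressly required again at the second event.

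A reader might infer that the table writes a recurrence stop wherever one is meant, because the pneumonitis row has "2nd occurrence: Permanently discontinue". That line belongs to the Grade 1-2 entry, and Grade 3 or 4 pneumonitis is stopped at the first event. The line therefore says nothing about how a Grade 3 recurrence rule should appear in the other rows.

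Section 6.6.3.2 also relies on Figure 6-2, which is not visible in the text reviewed. The absence of a precedence rule can be stated only for the text shown.

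**Conclusion.** The conflict is real and should be corrected. For a recurrent identical Grade 3 irAE in Part 1B, the protocol gives both a permanent stop and a route to lower-dose re-treatment, and six of nine table rows lead to the second without a limit. It matters mainly for colitis and skin reactions, and for symptomatic Grade 3 endocrine events and Grade 3 hyperglycemia that meet DLT criteria after Cycle 1.

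A reader might infer that all six rows are equally exposed, that the protocol requires re-dosing, or that dose finding is compromised. The documents support none of these. The endocrine rows are largely narrowed by 6.6.2, re-treatment is optional, and DLT counts and the MTD do not depend on this step.

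The documents give no event rate, so how often the case would arise cannot be stated. Exposure is limited: SAP Table 4 lists two Part 1B cohorts, and SAP Section 3 says that Part 2 is no longer applicable. The conclusion assumes that Figure 6-2 contains no irAE exception, and that the thyroid row whose label was lost in text extraction is a separate row.

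**What to change.** Keep the stricter rule and state it in both places.

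- Add to 6.6.3.2: *For irAEs in Part 1B, the second- and third-occurrence re-treatment options do not apply to a recurrent Grade 3 irAE; BNT411 is permanently discontinued (see 6.6.4.1).*
- Add to the six Table 6-1 rows: *Recurrent Grade 3: permanently discontinue (6.6.4.1).*

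The added line must name Grade 3 only. Several endocrine cells cover Grades 3 and 4 together, and 6.6.4.1 exempts hormone-controlled endocrinopathies from its Grade 4 stop recommendation. A bare recurrence line would override that exemption. Figure 6-2 should be checked for agreement. Cross-references in 6.6.5 and 7.1.2 would help but are optional.

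The cost is one sentence and six short table entries.

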#### **6.6.4.2 Infusion-Related Reactions (IRRs)**

IRR is a general risk to be considered for any new compound administered intravenously irrelevant of its MoA. IRR is typically of immediate onset after the compound's administration. We cannot exclude the risk of IRR with BNT411 due to the given limited experience with BNT411.

The following treatment guidelines are provided below for patients who experience an IRR associated with administration of BNT411 treatment.

- Grade 1- If an IRR Grade 1 occurs, the infusion does not need to be interrupted and can be continued at the investigator's discretion at half the infusion rate under close medical supervision.
- Grade 2-3- If an IRR Grade 2 or Grade 3 occurs, the infusion should be interrupted and appropriate medical management instituted. The infusion may be re-started at the investigator's discretion at half the infusion rate under close medical supervision if symptoms have resolved to Grade ≤1 within an hour.
  - Patients who have experienced prior infusion related Grade 2 or Grade 3 reactions in the trial should be premedicated. Premedication to prevent IRR in subsequent infusions may be administered at the investigator's discretion according to local guidelines but preferably includes an antihistamine (e.g., diphenhydramine 50 mg orally twice daily [po] or equivalent antihistamine), acetaminophen/paracetamol (e.g. acetaminophen 500-1000 mg po or equivalent), and if considered necessary, patients should receive corticosteroids at a suggested maximum dose of 100 mg prednisone or equivalent.
  - o If the patient has a second Grade 3 IRR despite premedication, the infusion should be stopped and the patient should be withdrawn from treatment.
- Grade 4- If anaphylaxis or Grade 4 IRR occurs, administration of BNT411 should be discontinued immediately and permanently, and appropriate medical therapy should be administered.

#### Please note:

- At all times during BNT411 infusion, immediate emergency treatment of an anaphylactic reaction according to institutional standards must be assured. In order to treat possible anaphylactic reactions, for instance, dexamethasone 10 mg and epinephrine in a 1:1000 dilution or equivalents should always be available along with equipment for assisted ventilation.
- All premedication must be reported on the concomitant medication page in the eCRF.

## 6.6.5 Safety Stopping Criteria

#### Across all patients in both Part 1A and Part 1B, the following rules apply:

- 1. The trial will be paused for:
  - a. Any death possibly related to BNT411
  - b. Two Grade 4 AEs that are considered possibly, probably, or definitely related to BNT411

If a suspected DLT occurs, a SRC meeting will be held as rapidly as possible. In the meantime, dosing of the ongoing patients in that cohort will continue unless there is reason to suspect there is an unacceptable safety risk based on the nature and/or severity of the observed DLT.

The SRC will decide whether and when the trial can be restarted after approval of a substantial amendment by the regulatory authorities and EC; or with the sponsor's concurrence, whether the trial should be stopped. Further information on the SRC is described in Section 9.6 and in the SRC Charter.

# In individual patients, treatment with BNT411 should be discontinued due to safety concerns under the following conditions:

- 1. If the patient experiences an AE fulfilling the DLT criteria.
- 2. If the patient experiences an AE that fulfils the DLT criteria after the DLT period has ended in the dose-escalation or during the expansion phase, but that fails to resolve to Grade ≤1 within 21 days after the planned dosing date or any other dose delay of more than 21 days due to toxicity possibly related to BNT411, unless otherwise approved by the sponsor's medical monitor
- 3. In case of a drug-related or life-threatening Grade 4 AE that does not fulfill the DLT criteria (excluding asymptomatic Grade 4 elevations in non-hematological laboratory values that resolve to Grade ≤2 within 14 days [± medical intervention]) unless otherwise approved by the sponsor's medical monitor.
- 4. If more than two dose reductions are required.
- 5. Patients with any eye disorders Grade ≥3, especially the occurrence of retinal detachment and marked decrease in visual acuity.
- 6. In case of cytokine release syndrome (CRS) Grade 4, the patient should be discontinued from treatment.
- 7. Second occurrence of an IRR of Grade ≥3 despite premedication prior to second infusion.
- 8. First occurrence of anaphylaxis or Grade 4 IRR.

#### Please note:

Patients should, whenever possible, irrespective of the reason for discontinuation, be examined as soon as possible.

#### 6.6.6 Safety Alert Communication Plan

Safety data such as DLTs, SAEs, SUSARs, or safety-relevant protocol deviations which may impact all patients in the trial will be communicated by the medical monitor through "Safety Alert Email" to the investigators and site staff to inform them about abovementioned safety issues. If recruitment has to be suspended, or dosing to be withheld in all patients, this countermeasure will be detailed in the safety alert email. If necessary, the email will also give guidance to the Investigators to promptly contact the patients and inform about any safety issue which may require patients to come for unplanned visit or any other measures as appropriate. If the email is not acknowledged, the site will be telephoned until contact is made with appropriate site staff. Furthermore, a SRC meeting will be held as rapidly as possible. Investigators and site

staff who do not attend SRC meetings will be provided with an email update of all SRC decisions within 24 hours of each meeting.

## 6.6.7 Atezolizumab Dose Modification and Management of Specific Adverse Events

Dose modifications for atezolizumab are permitted according to the atezolizumab Prescribing Information valid in a given country and local standard-of-care. Management of specific adverse events should be done according to the atezolizumab Prescribing Information and local standard of care.

## 6.6.8 Carboplatin Dose Modification and Management of Specific Adverse Events

Dose modifications for carboplatin are permitted according to the carboplatin Prescribing Information valid in a given country and local standard-of-care. Management of specific adverse events should be done according to the carboplatin Prescribing Information and local standard of care.

#### 6.6.9 Etoposide Dose Modification and Management of Specific Adverse Events

Dose modifications for etoposide are permitted according to the etoposide Prescribing Information valid in a given country and local standard-of-care. Management of specific adverse events should be done according to the etoposide Prescribing Information and local standard of care.

#### 6.7 Treatment after the End of the Trial

Patients who show some level of clinical benefit during the trial may be permitted to receive further cycles of treatment if discussed with the sponsor.

# 7 Discontinuation of Trial Treatment and Patient Discontinuation/Withdrawal

#### 7.1 Discontinuation of Trial Treatment

Patients will receive BNT411 treatment until one of the predefined discontinuation of treatment criteria has been met:

- Radiographic disease progression per RECIST 1.1 (Section 8.5.1) or confirmed radiographic disease progression by iRECIST (if applicable),
- Death,
- Unacceptable AEs requiring BNT411 discontinuation (refer to Safety Stopping Criteria Section 6.6.5),
- Investigator believes that it is in the best interest of the patient to stop BNT411 treatment,
- Withdrawal of consent,
- Pregnancy
- Lost to follow-up

If BNT411 treatment is permanently discontinued for other reasons than radiographic disease progression, every effort should be made to continue tumor assessments.

Further information on discontinuation of atezolizumab, carboplatin and etoposide should be referred to the respective SmPC or USPI.

Patients should, whenever possible, irrespective of the reason for discontinuation, be examined as soon as possible and the treatment discontinuation visit should be performed (Section 8.3).

